5.0 STATISTICAL CONSIDERATIONS

We will evaluate the data per recommendations of our statistician by categorical and continuous statistical testing, as applicable. For the primary outcomes of percentage change in hand volume from baseline after tourniquet application, and secondary outcome of residual volume as a percentage of baseline following limb positioning, we will compare the healthy contralateral arm versus the arm status post ALND. Paired t-tests will be used to compare measures averaged to produce a single pre-tourniquet hand volume and a single post-tourniquet hand volume. The differences will again be compared between patients' arms ipsilateral and contralateral to the side of ALND. Linear mixed effects model will also be fitted to account for the correlations between measurements on the same subject and history of ALND, arm position after tourniquet use, and patient-specific risk factors. This specific issue power analysis is further discussed below (5.3).

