4.0 MATERIAL AND METHODS

Study participants will be seated and patients' arms ipsilateral to prior axillary lymph node dissection will be elevated with the hand above the level of the ipsilateral shoulder for 15 minutes. This is to ensure an accurate baseline in all participants. Hand volume will be measured by aqueous volumeter to the level of the proximal wrist crease for a baseline. A tourniquet will then be placed on each study participant's upper arm, again ipsilateral to prior axillary lymph node dissection. This will be inflated to 40 mmHg for 25 minutes, after which hand volume will be again measured as described above. The limb will then be placed in an elevated position at shoulder height or in a sling at the waist, and hand edema will again be measured. The process will be repeated for each limb position after a 15-minute break time. The two limb positions are "sling," with the hand at the level of the waist, and "elevated" with the hand at the level of the shoulder. This will be repeated for the contralateral, healthy arm which will serve as an internal control.

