5.1 Outcome Measurements

Study participants will be evaluated prior to and following the above process.

Data collection:

- A. Demographic will be recorded: Age, sex, height, weight, BMI, comorbidities, number of lymph nodes excised in ALND, and presence of lymphedema
- B. Procedural measures: hand volume and percent change

Primary outcome: percentage change in hand volume from baseline after tourniquet application

Secondary outcome: residual volume as a percentage of baseline following limb positioning after tourniquet use

- C. Tourniquet complications: unresolved edema (i.e. persistent swelling lasting greater than the 30 minute evaluation period), petechiae (i.e. pinpoint skin redness or purple color caused by a minor bleed from broken capillary blood vessels), pain, paresthesias (tingling sensation), palsy (neurologic change related to peripheral nerve compression), by direct visualization and neurologic evaluation by a medical provider at the time of tourniquet use

Acute or delayed symptoms related to tourniquet use will be assessed and managed with routine care. Participants may contact the study staff at any time regarding delayed complication.

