5.2 Analysis plan

Data will be analyzed as above. To reiterate the methods (Section 4.0), a baseline volume will be measured in all participants prior to tourniquet use. The absolute change in hand volume, percentage change from baseline, and residual volume as a percentage of baseline immediately following tourniquet use will then be measured in all patients. The mean will be compared between the arms ipsilateral and contralateral to the side of ALND by paired t-tests. The parameters listed above are the primary outcomes. Each participant will then be monitored in two limb positions (elevated and sling as described above), with measurements taken on both arms ipsilateral and contralateral to the side of

ALND. Volume is measured after each position. The change in limb edema as a factor of time will be analyzed by a linear mixed effects model. This is the secondary outcome.

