5.3 Sample size

We analyzed preliminary data on percent change in hand volume in normal controls as a response to the application of a tourniquet. Similar data is not available in the literature for patients following ALND. In the pilot, the median change was 9.1%, with a standard deviation of 1.6% assuming each subject contributed one baseline hand volume and one volume following the application of the tourniquet.

Our scientific hypothesis is that the difference in change of mean hand volume among women who have had lymph node dissection, between the arms ipsilateral and contralateral to the side of ALND is zero or negligible. We therefore seek a sample size that expresses non-inferiority between ipsilateral and contralateral arms. In the absence of clinical norms for the margin of non-inferiority, we made the sample size calculation on the basis of margin of non-inferiority of 1% (in units of percent change in hand volume).

We plan to accrue 45 extremities in each group, with two arms per patient. We have 90% power that the upper 95% confidence interval of the difference will be at or below the stipulated margin of 1%. A confidence bound above the stipulated margin will be taken as evidence of some difference between ipsilateral and contralateral arms, indicating an effect of the prior axillary lymph node dissection over and above the effect of the tourniquet.

The above calculation assumed a standard deviation of 1.6 percentage point, and 45 patients with two arms each (ipsilateral and contralateral to ALND) to provide 90% power for a margin of equivalence of one percentage point using a two-sided significance level of 5%, with a primary endpoint of percentage change from baseline following tourniquet use. If 10% of patients are uninformative (N=40 for ipsilateral and contralateral arms), we expect have 87% power for the same margin of equivalence. If 20% are uninformative (N=35 for ipsilateral and contralateral arms), we would have 82% power. The secondary outcome of residual limb volume following elevation in the two limb positions (elevated and sling) are not included in this power analysis and are not primary outcomes.

We expect the study to begin upon approval, and conclude after recruitment in approximately 6-12 months.

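### Does the unnamed averaging in section 5.0 leave the primary comparison open to carry-over from the first tourniquet run?

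*Combined protocol and SAP*

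**What the plan says.** Section 5.0 sets the primary comparison: "Paired t-tests will be used to compare measures averaged to produce a single pre-tourniquet hand volume and a single post-tourniquet hand volume". The measures that enter the average are not identified.

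Section 4.0 describes 15 minutes of elevation, a baseline volume, 25 minutes of tourniquet, a second volume, and then a limb position: "The limb will then be placed in an elevated position at shoulder height or in a sling at the waist". It adds: "The process will be repeated for each limb position after a 15-minute break time". Read in full, this gives two baselines and two post-tourniquet volumes per arm. Replicate volumeter readings are not mentioned anywhere.

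Section 5.2 summarises the sequence more briefly. It says that "a baseline volume will be measured in all participants prior to tourniquet use", and after the tourniquet measurement that "Each participant will then be monitored in two limb positions". Section 5.3 takes the pilot SD of 1.6 "assuming each subject contributed one baseline hand volume and one volume following the application of the tourniquet". The secondary outcome in section 5.1 is "residual volume as a percentage of baseline following limb positioning after tourniquet use". The mixed model in section 5.0 also accounts for "arm position after tourniquet use, and patient-specific risk factors".

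**The concern.** An average needs at least two readings, and the only repeats described are the two runs. If those are pooled, the second baseline is taken in a hand that has already been swollen once. Section 2.0 says that the time swelling takes to subside in these patients is not known, so full recovery cannot be taken for granted. Slower clearance on the dissected side is also the kind of difference the trial is meant to detect.

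No planned measure looks directly at the second baseline. Residual volume is taken at the end of positioning, before the break. Unresolved edema is recorded as a complication and not as a volume at the start of run two.

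The non-inferiority conclusion depends on a margin of 1 percentage point. A shift of half a point towards the margin would cost much of the power, and a shift away from it would make a false claim of non-inferiority more likely. An undefined average also leaves an analyst a choice between the first run, the two-run mean and replicate readings.

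**Working it through.** **Inputs from section 5.3.** 45 patients with both arms, SD 1.6, pilot median change 9.1%, margin 1 point, two-sided 5% (one-sided 2.5% for the upper bound). Everything else below is an assumption.

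**The plan's own power.** With SE = 1.6 × √(2/45) = 0.337, power at a true difference of 0 is Φ(1/0.337 − 1.645) = 90.7%. The same formula gives 87.5% at N=40 and 83.4% at N=35. The stated figures of 90%, 87% and 82% therefore reproduce, as a one-sided 5% calculation with independent arms. (At one-sided 2.5% the result for 45 is 84.3%; that is a separate matter.) The averaging rule enters only through what the 1.6 represents.

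**Time before the second baseline.** If positioning lasts the 30 minutes that section 5.1 implies, the second baseline comes 30 + 15 = 45 minutes after release. If the elevation is repeated as part of the process, it comes at 60 minutes.

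**Bias if the runs are pooled.** Set the first baseline to 1 and the first post-tourniquet volume to 1.091. The second ipsilateral baseline is 1 + d/100, with no residual in the contralateral arm. Averaged change = (mean of the two post volumes)/(mean of the two baselines) − 1. With d = 1:

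| Second post-tourniquet volume | Averaged change | Bias (points) |
|---|---|---|
| Capped at 1.091 | 2.182/2.01 − 1 = 8.557% | −0.54 |
| Halfway, 1.096 | 2.187/2.01 − 1 = 8.806% | −0.29 |
| Additive, 1.101 | 2.192/2.01 − 1 = 9.055% | −0.05 |
| Proportional, 1.091 × 1.01 | 9.100% | 0 |
| Additive plus 0.5 | 2.197/2.01 − 1 = 9.303% | +0.20 |
| Additive plus 1 | 2.202/2.01 − 1 = 9.552% | +0.45 |

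In the capped case, d = 0.25, 0.5 and 2 give −0.14, −0.27 and −1.08. Equal residual in both arms gives 0. Residual in the contralateral arm only reverses the signs.

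**Effect on the decision.** The SD of a two-run average is 1.6 × √((1+r)/2), which is 1.29 at r = 0.3 and 1.56 at r = 0.9. The SD of the paired difference is that SD × √(2(1−ρ)), with between-arm correlation ρ of 0 or 0.5. The results use a noncentral t with 44 degrees of freedom and one-sided 2.5%.

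- False non-inferiority at a true difference of 1 point: capped 36% to 79%, halfway 14% to 32%, additive 3.4% to 4.2%, proportional 2.5%. Capped with d = 0.25: 6% to 10%.
- Power at a true difference of 0: unbiased 85% to 99.9%; with +0.20, 66% to 98%; with +0.45, 37% to 80%.

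**Cost of a first-run primary outcome.** If 1.6 is the SD of a single-run change, first-run power is 82.6% at ρ = 0 against 84.5% to 94.9% for the average, a loss of 2 to 12 points. At ρ = 0.5 it is 98.4% against 98.8% to 99.9%. Section 2.0 shows that the pilot used three postures, so each pilot subject's pair may itself be an average. In that case the single-run SD is 1.6/√((1+r)/2), or 1.64 to 1.98, and first-run power is 65% to 81% at ρ = 0 and 91% to 98% at ρ = 0.5.

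**The case for a change.** The strongest case for a change is that the primary outcome should have one definition before data are seen, and that a sentence would supply it. A first-run outcome comes before any positioning, so neither position order nor carry-over from an earlier run in the same arm can affect it, and its error stays at 2.5% in every scenario above. It also fits the one-pair basis given for the SD.

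Part of this stands. The measures are not named, and no passage compares the second baseline with the first. But sections 5.2 and 5.3 do not contradict section 5.0. Reducing several readings to one pre/post pair is compatible with a baseline taken before the tourniquet and with an SD expressed per pair. The lack is one of detail.

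The claim that a first-run outcome matches the SD is not secure, given the pilot's several postures. The design also has its own answer to carry-over: positioning, a break and, if the whole process is repeated, renewed elevation, whose stated purpose is a sound baseline. That is mitigation and not verification, but it makes a 1-point between-arm residual (1/9.1, about 11% of the pilot swelling) a demanding assumption.

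Position order and a possible run term concern the secondary mixed model. With one fixed order, run and position could not be separated anyway.

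**Conclusion.** No change to the plan follows. Section 5.0 leaves a definition unnamed, and the analyst can fill it sensibly by stating whether replicate readings or the two runs were averaged. If replicates within one run are meant, the carry-over question does not arise for the primary outcome.

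If the runs are pooled, the large error rates depend on a chain of assumptions: swelling still present after 45 to 60 minutes, more of it in one arm, and a second response that departs from both the additive and the proportional pattern. The documents give no evidence on occurrence, direction or size. Under the additive and proportional patterns the effect is at most 0.05 points for a 1-point residual.

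Choosing the first run in place of the average exchanges up to 12 points of power, or more if the pilot SD is already an average, for protection against a bias not shown to exist. Either choice is defensible and belongs to the trial's statistician. Tabulating second minus first baseline by arm, or giving a first-run result beside the pooled one, would be useful description if the runs are pooled, but it alters no stated rule or conclusion.

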5.1 Outcome Measurements

Study participants will be evaluated prior to and following the above process.

Data collection:

- A. Demographic will be recorded: Age, sex, height, weight, BMI, comorbidities, number of lymph nodes excised in ALND, and presence of lymphedema
- B. Procedural measures: hand volume and percent change

Primary outcome: percentage change in hand volume from baseline after tourniquet application

Secondary outcome: residual volume as a percentage of baseline following limb positioning after tourniquet use

- C. Tourniquet complications: unresolved edema (i.e. persistent swelling lasting greater than the 30 minute evaluation period), petechiae (i.e. pinpoint skin redness or purple color caused by a minor bleed from broken capillary blood vessels), pain, paresthesias (tingling sensation), palsy (neurologic change related to peripheral nerve compression), by direct visualization and neurologic evaluation by a medical provider at the time of tourniquet use

Acute or delayed symptoms related to tourniquet use will be assessed and managed with routine care. Participants may contact the study staff at any time regarding delayed complication.

5.2 Analysis plan

Data will be analyzed as above. To reiterate the methods (Section 4.0), a baseline volume will be measured in all participants prior to tourniquet use. The absolute change in hand volume, percentage change from baseline, and residual volume as a percentage of baseline immediately following tourniquet use will then be measured in all patients. The mean will be compared between the arms ipsilateral and contralateral to the side of ALND by paired t-tests. The parameters listed above are the primary outcomes. Each participant will then be monitored in two limb positions (elevated and sling as described above), with measurements taken on both arms ipsilateral and contralateral to the side of

ALND. Volume is measured after each position. The change in limb edema as a factor of time will be analyzed by a linear mixed effects model. This is the secondary outcome.

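### Section 5.3 reads a failed non-inferiority bound as an effect of the lymph node dissection, and Section 5.2 names primary outcomes that the rest of the plan does not

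*Combined protocol and SAP*

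**What the plan says.** Section 5.3 holds the only decision rule. Its margin is 1 point, in units of percent change in hand volume, and the success criterion is one-sided: "We have 90% power that the upper 95% confidence interval of the difference will be at or below the stipulated margin of 1" percent. On failure it continues: "A confidence bound above the stipulated margin will be taken as evidence of some difference between ipsilateral and contralateral arms". The sentence then attributes that difference to the earlier surgery, in the words "indicating an effect of the prior axillary lymph node dissection over and above the effect of the tourniquet". The same section calls the 1-point margin both one of non-inferiority and one of equivalence, and gives a two-sided 5% significance level.

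On the primary outcome, Section 5.1 is singular: "Primary outcome: percentage change in hand volume from baseline after tourniquet application". Section 5.0 attaches the label to the same measure ("For the primary outcomes of percentage change in hand volume from baseline after tourniquet application"), and Section 5.3 powers on it alone. Section 5.2 instead lists "The absolute change in hand volume, percentage change from baseline, and residual volume as a percentage of baseline immediately following tourniquet use", and then says "The parameters listed above are the primary outcomes". Its test is stated without a margin or a bound: "The mean will be compared between the arms ipsilateral and contralateral to the side of ALND by paired t-tests".

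**The concern.** A non-inferiority comparison has a valid conclusion when the bound falls at or below the margin. When it does not, the data may still be compatible with no difference at all. Section 5.3 turns that inconclusive result into a positive finding about ALND. For any true difference below 1 point, losing patients then makes an ALND effect easier to declare. The error runs toward claiming harm from the dissection. Section 2.0 says that these patients are already commonly steered away from elective hand surgery, so a spurious effect could reinforce that practice.

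The outcome list in Section 5.2 compounds this. Absolute change is measured in volume, so the margin is not defined for it and there is no rule for success. An analyst who works from Section 5.2 alone would test each parameter against zero, and could reach a different conclusion from one who applies Section 5.3 to the same data.

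**Working it through.** **Inputs.** From Section 5.3: margin 1 point; SD 1.6 points (pilot, one change per subject, so taken as the SD for one arm); N = 45, 40 and 35 patients; stated power 90%, 87% and 82%; hypothesized difference zero or negligible, taken as 0. Not given: the within-patient correlation r between the two arms' percentage changes. The values of r below are assumptions.

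**1. Reproducing the stated power.** SD of the paired difference = 1.6 × √(2(1 − r)), which is 2.263 at r = 0. At N = 45, SE = 2.263/√45 = 0.337. Power is the probability that a noncentral t (N − 1 df, noncentrality 1/SE) exceeds the critical t; for equivalence, both bounds must lie within the margin.

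| Reading, r = 0 | N=45 | N=40 | N=35 |
|---|---|---|---|
| Stated in Section 5.3 | 90% | 87% | 82% |
| One-sided 5% bound | 89.9% | 86.5% | 82.0% |
| Upper limit of two-sided 95% interval | 82.6% | 77.8% | 71.9% |
| Equivalence, two one-sided 5% tests | 79.7% | 72.9% | 64.1% |

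Only the one-sided 5% bound matches. Taking 1.6 as the SD of the paired difference (equal to r = 0.5) would give 99.3% at N = 45 with that bound, so the stated figures take no credit for pairing.

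**2. Chance of declaring an ALND effect when there is none.** At a true difference of 0 this is 1 − power, with the one-sided 5% bound:

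| Assumed r | SD of difference | N=45 | N=40 | N=35 |
|---|---|---|---|---|
| 0 | 2.263 | 10.1% | 13.5% | 18.0% |
| 0.25 | 1.960 | 4.2% | 6.3% | 9.5% |
| 0.5 | 1.600 | 0.7% | 1.3% | 2.4% |
| 0.7 | 1.239 | about 0.1% or less | about 0.1% or less | about 0.1% or less |

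The first row agrees with the plan's own figures: 100 − 90 = 10, 100 − 87 = 13, 100 − 82 = 18.

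**3. An example at N = 45, r = 0.** Observed difference 0.5: t = 0.5/0.337 = 1.48, two-sided p = 0.145, 95% interval −0.18 to 1.18. The one-sided bound is 0.5 + 0.567 = 1.07, so Section 5.3 declares an ALND effect where the paired t-test against zero finds none. At this SD, every observed difference from 0.433 to 0.680 behaves the same way.

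**4. The alternative rule.** Claiming greater ipsilateral swelling only when the two-sided 95% interval lies wholly above zero has a 2.5% error in that direction at any N or r. An interval that excludes zero in either direction carries 5%. The interval can lie above zero while the one-sided bound is at or below 1 point: about 2% of null trials at N = 45 and r = 0.5.

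**5. The outcome list.** Immediate residual percent = 100 × post/baseline = 100 + percentage change. The constant cancels in the paired difference, so its t-test is identical. The only distinct extra primary quantity in Section 5.2 is absolute change.

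**The case against.** The strongest case against is that the size of the problem is unknown and that much of the rest is wording. Most of that is fair, and it rules out several stronger conclusions that a reader might infer but the documents do not support.

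- *The plan has a 10–18% false-claim rate.* That needs the one-sided 5% bound and uncorrelated arms. The design is paired within patient, no correlation is given, and at r = 0.5 the rate is 2.4% or less. In the other direction, if the two-sided 5% level in Section 5.3 is meant literally, the rate at r = 0 is about 17%, 22% and 28% (100 minus 82.6, 77.8 and 71.9).
- *The replacement rule always lowers the error.* It does not. On the one-sided reading, at r = 0.5 or more, the current rule already errs at or below about 2.5%.
- *Section 5.2 creates three separate primary tests.* One is a restatement of another. The two that remain are correlated, and Section 5.0 also uses the plural for percentage change alone, which suggests loose usage. No sizeable multiplicity problem has been shown.
- *The margin is missing from the analysis.* It is in Section 5.3, Section 5.0 refers the reader there, and a paired t analysis can supply the bound. This part is mostly placement, and the equivalence wording in Section 2.0 is a background hypothesis, not a test specification.

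What survives is that the sentence in Section 5.3 is a wrong inference at every correlation, and that Section 5.2 contradicts three other sections on what is primary.

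**Conclusion.** The point holds and should be fixed. The failed-margin sentence in Section 5.3 is wrong as written. Its practical size depends on a correlation that the plan does not give: material if the arms are weakly correlated, as the stated power implicitly assumes, and small at 0.5 or above. The case for the change is that the conclusion becomes valid, not that the error rate always falls. The Section 5.2 label is an internal contradiction that can be settled in favour of percentage change, since Sections 5.0, 5.1 and 5.3 all point there. The power claim stands for a one-sided 5% non-inferiority bound with uncorrelated arms. On that same assumption about the arms, it does not stand for the two-sided level or the equivalence margin that Section 5.3 also names. Nothing here shows that the trial is too small for its one-sided rule, or that it would wrongly reassure.

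**What to change.** - **Section 5.3, failed margin.** Replace the sentence with *non-inferiority not shown*. Claim greater swelling in the ipsilateral arm only if the two-sided 95% confidence interval for ipsilateral minus contralateral lies wholly above zero. State that an interval above zero with the upper bound at or below 1 point is reported as a difference smaller than the margin.
- **Section 5.2, outcomes.** Make percentage change from baseline immediately after the tourniquet the sole primary outcome, and compare the upper bound of its paired mean difference with +1 point. Make absolute change secondary and drop immediate residual percent from the primary list.
- **Section 5.3, level and terms.** Choose one rule and use one term for the margin. For a one-sided 5% non-inferiority bound, 90/87/82% stands. For the upper limit of a two-sided 95% interval, restate power as about 83/78/72%. For equivalence by two one-sided 5% tests, restate it as about 80/73/64%. These are at correlation 0 and are higher if the arms are positively correlated.

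The cost is wording in Sections 5.2 and 5.3 and one sponsor decision on the level and on non-inferiority versus equivalence. No new data are needed, and N = 45 and its stated power are unchanged if the one-sided bound is kept.
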